- *Research Repositories*: If the purpose of this submission is to establish a Research Repository (bank, registry) and the material you plan to collect is already available from a commercial supplier, clinical lab, or established IRB approved research repository, provide scientific justification for establishing an additional repository collecting duplicate material. Describe the repository design and operating procedures. For relevant information to include, see the [UK Research Biospecimen Bank Guidance](#) or the [UK Research Registry Guidance](#).

This study will incorporate a prospective and a retrospective section:

The prospective study will be an uncontrolled open-label clinical trial.

The retrospective component will extract previously collected archival data from medical records of patients that started MAD therapy for OSA at the Orofacial Pain Clinic (Kentucky Clinic). These subjects had a second sleep study performed to assess the effectiveness of the mandibular advancement devices.

Attachments

Subject Recruitment Methods & Advertising

Describe how the study team will identify and recruit subjects. Please consider the following items and provide additional information as needed so that the IRB can follow each step of the recruitment process.

- How will the study team identify potential participants?
- Who will first contact the potential subjects, and how?
- Will you use advertisements? If so, how will you distribute those?
- How and where will the research team meet with potential participants?
- If applicable, describe proposed outreach programs for recruiting women, minorities, or disparate populations.
- How will minimize undue influence in recruitment?
- Attach copies of all recruiting and advertising materials (emails, verbal scripts, flyers, posts, messages, etc.).

For additional information on recruiting and advertising:

- [IRB Application Instructions - Advertisements](#)
- [PI Guide to Identification and Recruitment of Human Subjects for Research](#)

PROSPECTIVE SECTION:

We will recruit participants from the consecutive patients referred to the Orofacial Pain Clinic (OPFC) for the management of obstructive sleep apnea (OSA) with a mandibular advancement device (MAD). As part of the standard clinical protocols, these patients are initially evaluated for eligibility to start OSA therapy with a mandibular advancement device by the residents under supervision of an attending (provider) of the Orofacial Pain Division (College of Dentistry – University of Kentucky) at the OPFC. The PI, [name] is one of the attendings. After this evaluation, if the patient is eligible to start MAD therapy, they will be offered to continue with the standard of care at the clinic or to be evaluated to participate in this study. If the patient decides to proceed and evaluated for eligibility for this study, the initial assessment will be done by [name] [name], or by [name] [name], or by [name] [name]. If the patient is eligible and agrees to participate, verbal consent will be obtained and all forms will be completed. After consent, the following sessions will be performed at the OPFC (UK Kentucky Clinic) or at the Delta Dental of Kentucky Clinical Research Center (College of Dentistry - University of Kentucky).

In order to offer the Orthoapnea NOA® device to eligible subjects that might like to participate, a report will be requested from Clinical data routinely collected in RedCap to identify patients that were evaluated within the last 3 yrs and referred to [name] [name] for MAD therapy but did not return to start treatment. Those patients will be contacted via phone by [name] [name] or by [name] [name] (see phone script attached) to explain the study. If the patient is interested in participating in the study, an appointment will be scheduled to do an evaluation and initial assessment for eligibility for with [name] [name] or with [name] [name]. The treatment relationship that [name] [name] has with those patient was only based on the initial evaluation performed, with no other sessions nor procedures conducted. There is no treatment relationship between [name] [name] and those patients. Historically, there is a considerable number of patients that never started treatment because it was not covered by their insurance. So this recruitment will target and benefit a population with less access to health care. Contact with the participants for recruitment, scheduling and clinical sessions, will be carried out by [name] [name], [name] [name] and/or [name] [name].

Internet and Social Media: This study will be advertised on recruitment internet webpages in digital or video form (e.g., UKclinicalresearch.com, ResearchMatch.org, UK Public Relations and HealthCare, CCTS and may utilize Google Adwords). The study will be promoted via social media, including Facebook boost ads, UK_CCTS Facebook, UK_CCTS Twitter, UK_CCTS Instagram, UKclinicalresearch_Youtube, UK and UKHC social media, and departmental/lab pages. If advertised on UKClinicalresearch.com, the online study flyer will include an option for interested individuals to enter and submit their contact information, they will be asked whether study team can contact them (Yes or No) via study related text messages, and CCTS will also ask, 'How did you learn about the study? Internet and social media recruitment will follow the terms of use for each site utilized. The study will also be promoted through UK HC monitor screens.

Research Participant Registries: Potential participants may be identified from registry databases, including but not limited to ResearchMatch.org*, WellnessHealthandYou.org, Sanders Brown Center on Aging, Infectious Disease, Dentistry, and the Markey Cancer Center. *ResearchMatch.org/uky will be utilized as a recruitment tool for this protocol. ResearchMatch.org/uky is a national electronic, web-based recruitment tool that was created through the Clinical & Translational Science Awards Consortium in 2009 and is maintained at Vanderbilt University as an IRB approved data repository (Vanderbilt University IRB #090207)." Once UK IRB approval is obtained the researcher or proxy will upload a flyer with no contact information via ResearchMatch email to selected de-identified participants in the ResearchMatch registry. If the de-identified participant selects "Yes, I'm interested!" the researcher or proxy will receive information about participant and they may contact them with more information about their research study. If the participant selects "No, thanks", researcher or proxy will not receive any information from de-identified participant.

Outreach activities: The CCTS attends outreach activities to promote research participation in general (e.g., Roots & Heritage Festival, Latino Festival, Eastern Kentucky University, Transylvania Health fairs, etc.) and will bring all relevant study flyers that are enrolling participants.

E-Newsletters and ListServs: This study may also go out on email distribution, listservs, or enewsletters, e.g., the CCTS list serv, Markey Cancer Affiliates list servs, ResearchMatch.org, Wednesday's Word, Kentucky Office of Rural Health (KORH), Appalachian Translational Research Network (ATRN), etc. Physician referral letters to community physicians for patient recruitment.

UK Public Relations (College/Dept. PR personnel) and UK HealthCare venues: Articles and interviews about the researchers and research study may be promoted via UKNow, Kentucky living, and other media outlets. Research and study-related articles published on UKNow may contain standard language directing interested individuals on where to read more about research and current studies: You can make a difference through participating in research and discovery. To find more information, including a list of current studies at UK and access to studies nationwide, please visit UKclinicalresearch.com or call [contact] or join the ResearchMatch.org or wellnesshealthandyou.org registries to be matched today. UKPR, UK HealthCare marketing or the CCTS PRS may create videos to promote research, researchers and their studies to local, regional and national media venues and on internal hospital monitors. UK HealthCare may place study recruitment flyers on their internal and external racks (e.g., UK pharmacies, clinics, UK Libraries and Lexington Libraries) or on digital monitors. Participants may be recruited using newsletters, such as In the Loop, Health Matters, Making a difference, and external news letters. The study may also be advertised through UKPR and UKHC outreach activities. UKHC and CCTS have booths at many events, and researchers and coordinators are invited to attend any events that pertain to their study populations. Researchers may participate in radio or TV interviews. General information about their research may be presented with a phone number or website url for more study specific information. Consenting members of the research team and/or consenting participants may be interviewed about the study for print, radio, or video which may be distributed via the aforementioned activities.

Attachments

Attach Type	File Name
Advertising	Advertisements 71295.docx
Advertising	DENT-036 MON stamped.pdf
Advertising	DENT-036 MON.pdf
Advertising	DENT-036 research match stamped.pdf
Advertising	DENT-036 research match.pdf
Advertising	DENT-036 social media stamped.pdf
Advertising	DENT-036_flyer.pdf
Advertising	DENT-036 social media.pdf
Advertising	DENT-036_flyer_stamped.pdf

Research Procedures

Describe how the research will be conducted.

- What experience will study participants have?
- What will study participants be expected to do?
- How long will the study last?
- Outline the schedule and timing of study procedures.
- Provide visit-by-visit listing of all procedures that will take place.
- Identify all procedures that will be carried out with each group of participants.
- Describe deception and debrief procedures if deception is involved.

Differentiate between procedures that involve standard/routine clinical care and those that will be performed specifically for this research project. List medications that are explicitly forbidden or permitted during study participation.

PROSPECTIVE SECTION:

An Orthoapnea NOA® (OrthoApnea® laboratory, Malaga, Spain; FDA K202651) appliance will be custom made for each participant. Digital impressions (scanner 3Shape TRIOS® 3 (does not involve any form of radiation)), protrusive records will be obtained at 50% from maximum retrusion (5 mm fork and George GaugeTM, and clinical pictures will be obtained following the protocol recommended by the manufacturer. Maximum opening will be measured adding the interincisal distance to the overbite (in millimeters, using TheraBite® Range of Motion ruler). Information will be uploaded in the laboratory software (Apneadock®) to order the appliance. The MAD will be fabricated at an initial protrusion of 50%, with subsequent progressive mandibular components of additional 10% of protrusion until 80% of the maximum protrusive is achieved. Lastly, a full coverage morning deprogrammer (TAP® AM Aligner - Airway Management Inc) will be fabricated for all the participants to be used for 10 minutes upon removal of the MAD. Verbal and written instructions will be provided.

At the device delivery appointment, we will fabricate an aligner for the patient to wear for 10 minutes each morning after waking and removing the OrthoApnea NOA® oral appliance. The morning aligner (TAP® AM Aligner) is a record of the patient's habitual bite (the way the teeth come together normally) that will reposition their mandible back into its normal position. It is part of the standard of care for patients undergoing mandibular advancement (MAD) therapy. The aligner is constructed from a thermoplastic material that, when heated, can be molded by hand onto the upper or lower teeth. Once the thermoplastic material is molded around the teeth, they will be instructed to bite down while it is still soft. This will create indentations for the opposing teeth and allow them to be set at their 'normal' and proper biting position. After the molded thermoplastic material has hardened at normal temperature, it is removed from the mouth and trimmed, if needed.

Follow up sessions will be scheduled every two weeks until maximum therapeutic benefit is achieved. At each follow up visit patients will be asked to fill out a questionnaire and further advancement of the MAD will be determined by changes in patients' symptoms and Epworth Sleepiness Scale (ESS). Measures of successful management include: ESS < 10, and >70% reduction or absence of snoring, observed apneic events, and daytime fatigue, to be assessed via questionnaire using a numerical rating scale (NRS). Once the patient has obtained successful management of symptoms, 80% of maximum protrusive or is unable to tolerate the advancement, a home sleep apnea test (Alice NightOne, Phillips Respironics®) will be provided to the patient to perform one night while wearing the appliance to determine the efficacy of the MAD. We will verbally instruct the patient how to operate the machine, and a printed copy of the manufacturer protocol for patients will be provided. Additionally, we will provide our contact number if any question arise. An appointment will be scheduled in the following 2-3 days to return the machine, and to further advance the appliance if needed. Sleep parameters including: AHI, RDI, minimum and average oxygen saturation will be extracted from the initial PSG, and by a trained technician from the final home sleep apnea test, which will be scored following the American Academy of Sleep Medicine Scoring Manual.

The efficacy of the appliance for the management of OSA will be established based on two criteria. Criterion I: > 50% reduction of AHI/RDI. Criterion II: AHI/RDI < 5 events/hour or <15 events/hour with a significant reduction of OSA associates symptoms as defined before. Therapeutic failure will be established when at 100% of advancement of the device, there is less than 50% of reduction of the AHI/RDI with a residual AHI/RDI >5 events/hour with OSA associates symptoms.

If the criteria for success is reached, the participation of the patient in the present study will be ended. The subject will be offered to continue with standard of care in the OFPC for future follow-ups, and a report will be provided and sent to the treating sleep physician. The subject will be allowed to keep the appliance after the study is completed. If participants do not reach a successful management of OSA at 100% of advancement, they will be referred back to their referring sleep physician to consider another treatment option.

The participation in this research will last between seven to sixteen weeks depending on the time for each patient's individual improvement. The initial visit will last 45-60 minutes, and the follow-up sessions will take about 30-45 minutes. After participation in the study is completed, the participants will be allowed to keep the MAD and all the accessories provided by the manufacturer

RETROSPECTIVE SECTION:

Archival data will be extracted from records of patients that started MAD therapy for OSA at the Orofacial Pain Clinic (University of Kentucky) between 01/01/2010 and 08/17/2021. An active study involving MAD therapy outcomes (protocol #46643; same PI, [name] [name]) includes a consent form for the retrospective participants to collect retrospective data and future use of that data in future research projects. The data collection process of the previous study is being conducted using RED Cap (CCTS - University of Kentucky), and through that software, we intend to obtain a report to identify subjects that started MAD therapy and had a second sleep study performed to assess the effectiveness of the MAD. Data regarding demographic characteristics (age, gender, BMI and OSA

diagnosis), sleep parameters (AHI, RDI, minimum and average oxygen saturation), level of advancement of the MAD (%) prior to the second sleep study, and compliance of use will be extracted creating a deidentified "report" (spreadsheet) from the RED Cap database (assigning progressive numbers (starting with M51)).

Attachments

Data Collection & Research Materials

In this section, please provide the following:

- Describe all sources or methods for obtaining research materials about or from living individuals (such as specimens, records, surveys, interviews, participant observation, etc.), and explain why this information is needed to conduct the study.
- For each source or method described, please list or attach all data to be collected (such as genetic information, interview scripts, survey tools, data collection forms for existing data, etc.).
- If you will conduct a record or chart review, list the beginning and end dates of the records you will view.

This study has a prospective and a retrospective component. (SEE ANNEX IN ATTACHMENTS)

1) Prospective study: data will be obtained using paper questionnaires:

- Demographic information regarding age, race, gender and comorbidities will be extracted from the initial questionnaire (Annex 1).
- The self-reported use of MAD will be assessed at each follow-up via questionnaire on a five-point checklist (number hours per night and nights per week) (to be extracted from Annex 6).
- Epworth sleepiness scale (ESS) (Annex 1 and 6)
- Snoring, observed apneic events, and daytime fatigue, to be assessed via questionnaire using a numerical rating scale (NRS) (to be extracted from Annex 1 and 6).
- Sleep parameters including: AHI, RDI, minimum and average oxygen saturation will be extracted from the initial PSG, and by a trained technician from the final home sleep apnea test.
- The presence of signs, symptoms of TMD will be assessed following the Diagnostic Criteria for Temporomandibular Disorders (DC/TMD) Symptom Questionnaire and Examination Form (Annex 2 and 4).
- Additional parameters will be controlled, including the presence of morning headaches (to be evaluated via questionnaire at baseline and at each follow-up using NRS), waking up during the night to urinate (to be evaluated at baseline and at each follow-up via questionnaire using continuous numeric scale), and the sleep quality (will be assessed at baseline and when performing the home sleep apnea test, using the Pittsburgh Sleep Quality Index (PSQI) questionnaire). Patients subjective perception of improvement will be assessed at each follow up using visual analog scale (to be extracted from Annex 6).
- Incidence of side effects will be assessed at each follow-up session, including subjective increase/decrease salivation (measured via questionnaire using numeric rating scale), increase/decrease teeth mobility, changes in occlusal contacts (measured in habitual occlusion using 0.01 mm occlusal registration strips (ARTUS corporation®) (to be extracted from Annex 6&7).
- Problems related to the appliance will be measured at each follow up session, considering appliance breaks, cracks, deformation, retention changes, wear, discoloration changes and calculus accumulation (to be extracted from Annex 7).

2) Retrospective study: Archival data will be extracted from records of patients that started MAD therapy for OSA at the Orofacial Pain Clinic (University of Kentucky) between 01/01/2010 and 08/17/2021. An active study involving MAD therapy outcomes (protocol #46643; same PI, [name] [name]) includes a consent form for the retrospective participants to collect retrospective data that allows to use the obtained data in future research projects. The data collection process of the previous study is being conducted using RED Cap (CCTS - University of Kentucky), and through that software, we pretend to obtain a report to identify subjects that started MAD therapy and that had a second sleep study performed to assess the effectiveness of the MAD. Data regarding demographic characteristics (age, gender, BMI and OSA diagnosis), sleep parameters (AHI, RDI, minimum and average oxygen saturation), level of advancement of the MAD (%) prior to the second sleep study, and compliance of use will be extracted creating a deidentified "report" (spreadsheet) from the RED Cap database (assigning progressive numbers (starting with M51)).

Attachments

Attach Type	File Name
DataCollection	Annex MP Orthoapnea.docx

Resources

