Oral appliance therapy has been associated with various short and long-term side effects. In relation to the short-term adverse effects: hyper-salivation [7], dry mouth [7], dental pain [7], gingival irritation [7], and temporomandibular disorders [7] [8] has been reported at an incidence rate ranging between 6% to 86%. The long-term side effects include: temporomandibular disorders [7] [8], occlusal changes (ie: a reduction in overjet [9] [10], overbite [9] [10], and development of posterior open bite [8] [10] among others) and range between 0% and 75% of patients [7] [9] [10]. In a recent meta-analysis, the odds of experiencing a side effect leading to discontinuation of therapy with an oral appliances was 6.65:1 (95% CI) [1]. In previous studies, it has been demonstrated that an increase in side effects could be expected at larger advancement levels [11] [12], especially with more than 50% of mandibular protrusion [11]. Therefore, having a MAD design that requires less degree of mandibular advancement to reach an adequate management of OSA represents a great benefit for the patients, and can lead to better compliance.

In the case of the Orthoapnea NOA® device, the customization level is reached with a personalized approach based on clinical pictures, digital dental scans, and radiographic studies. Therefore, this allows a design that guides the mouth opening with a forward mandibular motion. The main target is to move the jaw forward progressively, so that the more the mouth is opened, the more forward the mandible can be positioned. Therefore, the Orthoapnea NOA® device is thought to require a less degree of advancement to be effective in the management of OSA than other designs. Consequently, comparing this particular characteristic of the Orthoapnea NOA® with the other available device design is hypothesized to be correlated with a lower incidence of side effects and better patient compliance.

FDA approved use: "NOA SLEEP APNEA AND SNORING DEVICE is a mandibular advance device (MAD) indicated for obstructive sleep apnea (OSA) and to alleviate or reduce snoring in adults." (FDA K202651 ; https://www.accessdata.fda.gov/cdrh_docs/pdf20/K202651.pdf). See attachments.

REFERENCES:

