Aim 1.1 was to assess the efficacy of the NOA® mandibular advancement device. To do this, we had two different criteria for success as defined before. For each of these criteria, we calculated the proportion of patients who “succeeded” vs. “failed.” As exploratory analyses, we used independent samples t-test or chi-square testes (as appropriate) to compare baseline demographic characteristics between those who succeeded and failed for each of the criteria. **Aim 1.2** was to describe the percentage of advancement (%) needed to reach efficacy for the NOA® appliance in the management of obstructive sleep apnea. For this aim, we only examined the data of those who “succeeded” in Aim 1.1. Paired samples t-tests were carried out to detect the possible statistically significant differences in each of the parameters studied before and after receiving the treatment. The sociodemographic characteristics and other variables of interest of the patients included in the prospective and retrospective studies were described (n, mean \pm SD).

Aim 2 was to describe patient compliance to the NOA® device in the management of obstructive sleep apnea. Using the definition of compliance provided above, we computed the proportion of study participants who complied with the NOA® appliance and described the use in terms of nights per week and hours per night (n, mean \pm SD).

Aim 3 was to assess the incidence and prevalence of temporomandibular disorder (TMD) diagnoses, morning headaches, possible sleep bruxism, nighttime voids, sleep quality, side effects, and of problems related to the NOA® appliance during the titration process by using paired samples t-test or chi-square testes (as appropriate) to compare baseline and final values between those who succeeded and failed for each of the criteria.

Mean and standard deviation and other centralization measures were calculated for quantitative variables, frequencies, and percentage values were calculated for categorical variables. The McNemar test was used as a significance test, with which assessed if there were significant changes. Statistical significance was defined by $p < 0.05$. All analyses were conducted using SPSS version 29.

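### Aim 1.2 describes the advancement needed in successes only, mainly by mean and SD, so the figure depends on who fails and can mislead beside other designs

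*Combined protocol and SAP*

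**What the plan says.** All places are in the combined protocol and SAP.

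- **Settings** (Research Procedures, prospective section): "The MAD will be fabricated at an initial protrusion of 50%, with subsequent progressive mandibular components of additional 10% of protrusion" and this continues "until 80% of the maximum protrusive is achieved". No lower setting is tried.
- **Titration** (same section): "further advancement of the MAD will be determined by changes in" symptoms and the Epworth score. The home sleep test comes at the end of titration: "Once the patient has obtained successful management of symptoms, 80% of maximum protrusive or is unable to tolerate the advancement".
- **Success and failure** (same section): two success criteria are given. Criterion I is a reduction in AHI/RDI; Criterion II is a residual AHI/RDI level, in one branch combined with symptom improvement. On failure the text says: "Therapeutic failure will be established when at 100% of advancement of the device".
- **Analysis set for Aim 1.2** (Statistical Methods): "For this aim, we only examined the data of those who" succeeded under Aim 1.1.
- **Summary measure** (Statistical Methods): none is named for advancement itself. The Aim 1.2 paragraph closes by describing variables of interest in both cohorts as n, mean and SD. A general sentence adds: "Mean and standard deviation and other centralization measures were calculated for quantitative variables".
- **Comparison**: Objective 1 includes a retrospective comparison with other designs, and the Background says that the device "is thought to require a less degree of advancement to be effective in the management of OSA than other designs". The Statistical Methods specify no between-device test of advancement.
- **Archive** (Subject Recruitment, retrospective section): the patients are those who had a second sleep study, and the advancement recorded is the level before that study.

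**The concern.** The claim that sets this device apart is that it works at less advancement than other designs. The figure meant to carry that claim is computed after the participants in whom the device did not work have been removed. Such a figure mixes two things: how far the device had to be advanced, and which patients it managed to help. A device that also succeeds in hard patients at the top of its range adds high values to the average. A device that fails in those patients adds nothing and keeps a low average. Set beside another design's average, the figure can point away from the more effective device.

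The Background also says that side effects increase especially above 50% protrusion. The useful quantity is therefore the share of all participants controlled at the 50% setting and at each later one. A mean over successes does not give it.

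**Working it through.** The plan gives no figure for advancement, so there is none to reproduce. The check is whether a success-only mean orders devices correctly.

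**Inputs.** The settings 50, 60, 70 and 80% come from Research Procedures. The 45 treated is the sample size in the subject-population section (the Statistical Methods give 33). The counts at each setting are assumed, because the documents give none.

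**Step 1: success-only mean.** Mean = Σ(setting × successes) / Σ successes.

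- Device A, with 20, 5, 3 and 2 successes: (20×50 + 5×60 + 3×70 + 2×80) / 30 = 1670/30 = 55.7%.
- Device B, the same with ten more successes at 80%: (20×50 + 5×60 + 3×70 + 12×80) / 40 = 2470/40 = 61.75%.

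**Step 2: cumulative success over all 45 treated.**

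| Final setting | A | B |
|---|---|---|
| 50% | 20/45 = 44% | 20/45 = 44% |
| at or below 60% | 25/45 = 56% | 25/45 = 56% |
| at or below 70% | 28/45 = 62% | 28/45 = 62% |
| at or below 80% | 30/45 = 67% | 40/45 = 89% |

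B equals A at the first three steps and exceeds it at the last, yet its mean is about 6 points higher. The median over all 45 (the 23rd patient) falls at the 60% step for both.

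**Step 3: why this is general.** Adding k successes at setting x to n successes with mean m changes the mean by k(x − m)/(n + k). Here that is 10 × (80 − 55.67)/40 = 6.1 points. Any added success above the current mean raises it. Conversely, a device that succeeds in only 10 of 45 (22%), all at 50%, would report a mean of 50%.

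**Step 4: the 50% floor.** As an illustration, assume that the true requirement is normal with SD 10 points, and record it on the ladder among those needing 80% or less.

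| True mean | Recorded mean, floor at 50% | Same 10-point steps, no floor | Successes at the floor |
|---|---|---|---|
| 40 | 51.8 | 45.0 | 84% |
| 50 | 56.8 | 55.0 | 50% |
| 60 | 64.7 | 64.4 | 16% |
| 70 | 71.9 | 71.9 | 3% |

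The floor matters when many patients need less than 50%. Above that, the recorded mean still falls as the requirement falls.

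**Step 5: what a recorded level means.** Advancement follows symptoms, and AHI/RDI is measured only once titration has stopped. A participant successful at 70% may already have met the AHI/RDI criterion at 60%. Every recorded level, not only the first, is an upper bound on the level needed.

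**The case against.** The strongest reply is that the aim itself conditions on success: a patient who never reaches efficacy has no observed level at which it was reached. Aim 1.2 is descriptive, no between-device test of advancement is specified, measures other than the mean are allowed, and Aim 1.1 reports success proportions for this device alongside. The counts in the illustration are invented, with all ten extra successes placed at 80%. All of this is fair. It lowers the weight of the point but does not remove it, because Objective 1 still intends a comparison and mean and SD are the only summary specifically offered in the Aim 1.2 paragraph.

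A reader might go further in three ways that the documents do not support.

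- *The floor prevents the study from showing a lower requirement.* The hypothesis is relative to other designs, and the Background cites published devices at 50% to 80%, which is this device's own range. A lower mean than a comparator can be shown there. The floor would count against this device only if comparators could be recorded below 50%, and the documents do not say so.
- *Those who do not succeed need more advancement and should be treated as right-censored.* Titration also stops for intolerance, possibly at a low setting, and some patients may not respond at any setting. Neither group is shown to need more, and stopping for intolerance is informative.
- *Recorded values can only be 50, 60, 70 or 80%.* The failure rule refers to 100% of the device's advancement, and further advancement is allowed after the sleep test. How these relate to the 80% limit is not explained.

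**Conclusion.** The point holds in a limited form. Restricting Aim 1.2 to successes makes the advancement figure depend on who fails, so a device that is never worse at any setting can appear to need more advancement. In the illustration the gap is 61.75 − 55.67 = 6.1 points. That size rests on assumed counts, and the documents do not show that such a reversal is likely. The direction follows from the arithmetic.

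The 50% floor is secondary: the mean cannot show a requirement below 50%, but it can show a lower requirement than a comparator within 50–80%. It would be wrong to infer that the plan already contains a biased formal test between devices. It contains an intended comparison and a summary that does not serve it well. This is a cheap improvement and does not invalidate the study.

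**What to change.** Change the wording of Aim 1.2 and add one table or figure. No starting position, step or clinical rule needs to change for this.

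1. For each success criterion, report the number and proportion of all participants given the device whose success was recorded at a final setting of 50%, and at or below 60%, 70% and 80%, with exact confidence intervals.
2. Keep every non-success in the denominator, including those who stop for intolerance. Use no right-censoring model.
3. State that each recorded level is where symptom-guided titration stopped, and is therefore an upper bound on the level needed.
4. Take any median from this distribution, reported as '50% or less' if more than half succeed at the first step and as 'not reached' if fewer than half succeed at all.
5. Present the archived devices the same way, stating that their denominator is only patients with a second sleep study. The listed extract contains AHI and RDI but no symptom scores, so the symptom branch of Criterion II cannot be applied there unless those data are added.
6. Reconcile the passages that give 80% of maximum protrusion with those that give 100% of the device's advancement, so that the last step is defined.

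For the prospective cohort the cost is SAP wording, since Aims 1.1 and 1.2 already require setting and success status. The downsides are that a distribution is quoted and not a single mean, and that the archive curve rests on a selected denominator.
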